### 12.2 Secondary Outcomes

#### Patient-Centered Outcomes (PCOs)

- 1) **Distress:** Oncology regulatory bodies recommend routine use of screening for *distress*, often referred to as the sixth vital sign in cancer care, as an integral part of comprehensive care (53). Distress is defined as “a multifactorial unpleasant emotional experience of a psychological, social and/or spiritual nature that may interfere with the ability to cope with cancer, its physical symptoms and treatment”(53). Elevated levels of distress are linked to reduced quality of life, poor adherence to treatment and even reduced survival (54-58). We selected the **Distress Thermometer (DT)**(59) as a simple and validated measure of *global distress* which is widely used in cancer studies. This one item instrument utilizes a figure and asks individuals to rate distress levels during the past week. Scores range on an 11-point scale from 0 (none) to 10 (extreme distress).
- 2) **Psychosocial needs assessment:** Standardized distress screening tools such as the DT are insufficient to pinpoint the specific problems contributing to stress (60). *Needs assessment* is a recommended strategy that focuses on identifying unresolved patient concerns contributing to distress (61) and lie at the core of our conceptual model for this proposed intervention. Assessment of needs is indicative of the gap between patient experiences and expectations. Our hypothesis was that a navigation intervention that detects and addresses socio-legal barriers will result in a reduction in perceived needs over time. While many validated needs assessment tools exist (62), the **Cancer Needs Inventory (CaNDI)** (63) was selected for several reasons: a) the 7 domains capture needs reported most commonly by our patient partners, b) the instrument has a 5th grade reading level, c) it had rigorous psychometric testing in diverse populations and d) it takes less than 8 minutes to complete (63). Patients rate the extent of their concern in the past two weeks with 39 items across the 7 domains (anxiety, depression, emotional, social, healthcare, practical and physical) on a scale from 1 (not a problem) to 5 (very severe problem). Items are

summed to create a total distress score (63). Based on feedback from both the Intervention and Control Navigator along with the Oncology Social Worker, we modified the CaNDI by deleting one question related to suicidality. During the early part of recruitment it was determined that the question was disruptive to patient care and thus our provider stakeholders recommended we drop the question. As a result the CaNDI instrument only included 38 questions.

- 3) **Patient satisfaction** reflects a core dimension of healthcare quality and patient-centered care (64-66). Patient satisfaction indicates the extent to which patients' healthcare experiences match their expectations (67, 68). The construct of patient satisfaction has been linked to health status, quality of life, and adherence to recommended treatment (69-71). The **Patient Satisfaction with Interpersonal Relationship with Navigator (PSN-I)**, a 9-item navigation-focused measure that produces a composite score to assess satisfaction with aspects of care in which navigation and has been validated in both English-speaking and Spanish-speaking populations (72). This survey instrument was administered at the 6 and 12 month follow ups interview.
  
- 4) **Case Cancer Self-efficacy**; measure of patient's confidence in understanding and participating, maintaining a positive attitude and seeking and obtaining information surrounding their cancer care. It is a 12 item survey (scale 1-4) with 3 domains: seeking and obtaining information, understanding and participating in care, and maintaining a positive attitude. Add responses to create score for each subscale & total scale; higher score=higher self-efficacy

### 13. Participant timeline

#### Data collection forms

Study forms will be administered by a Research Assistant (RA) at the following study time points: Baseline, 3, 6 and 12 months follow-up. RAs will work with the patient to schedule study visits to coincide with patient's clinic visits.

Form	Study Time period			
	Baseline	3 month	6 months	12 months
General legal screen (I-HELP)	X	X	X	X
Cancer Needs Distress Inventory (CaNDI)	X		X	X
4-item Brief health literacy Screening Tool (BRIEF)	X			
Distress Thermometer (DT)	X	X	X	X
Communication and Attitudinal Self-Efficacy (CASE)- Cancer	X		X	X
Employment Baseline Questions	X			
Berkman-Syme Social Support Survey (added to protocol January 2015)	X	X		
MOS (added to protocol January 2015)	X	X		
Detailed Legal Screen*	X	X		
Level of Legal Need*	X	X		
Patient Satisfaction with Navigation			X	X

\*Intervention arm only

## 14. Sample Size

Sample size estimates for the clinically relevant outcomes are based on the primary metric: **timely initiation of primary treatment**, a dichotomous outcome (yes/no) calculated for each subject. Since clinical outcomes will be derived from the medical record, we do not anticipate any loss to follow up on these outcomes. We anticipate our study will have 80% power of detecting an advantage to navigation enhanced by a medical-legal partnership, if the enhanced intervention raises the percent in each group receiving timely initiation of care from 76% to 90.5% (testing at the two-tailed .05 level) from patient navigation alone to legal navigation. Comparison of the two study groups on our secondary outcome of time to initiation of cancer treatment, or the number of days to the start of treatment, through survival analysis, takes advantage of more information and should provide somewhat greater power. For example, given the above scenario, (76% vs. 90.5% initiation of care by 90 days) and assuming a constant hazard, (i.e., exponential survival), a log rank test gives 86% power of detecting a difference between the two study groups.

Second, we will conduct separate analyses for the breast and lung cancer participants.

## 15. Recruitment

Working with oncology providers, Project SUPPORT research assistants approached individuals meeting the eligibility requirements on the day they received their cancer diagnosis or shortly thereafter. Once the physician had met and discussed the diagnosis with the patient, a research assistant who spoke the patient's language (English, Spanish, or Haitian Creole) introduced the study using the informed consent as a guide. The patient was presented with a brief description of the study, a copy of the informed consent and would decide whether they would like to discuss the study further or have the research assistant contact them at another time. Research assistants followed up with those patients that were eligible and interested in participating until they made a decision about enrollment or exceeded the 30 day period from diagnosis to be enrolled. The research team maintained a presence in clinic and engaged both the new and existing providers at tumor board conference and through frequent email communication.

## Assignment of interventions

### 16. Allocation

- 1) Comparison of study groups on demographic and clinical characteristics will be done to assess the success of randomization. With our stratified blocked randomization scheme, treatment groups will be balanced with regard to gender, insurance (public/private) and race (white/non-white) in a manner proportionate to those in the study population.
- 2) To ensure balanced group assignment on key demographic characteristics, randomization for Breast Cancer patient (females only) will be based on race (white/nonwhite) and insurance status (private/public) resulting in the following strata:
  - a. White, Private insurance
  - b. White, Public insurance
  - c. Nonwhite, Private insurance
  - d. Nonwhite, Public insurance

- 3) If differences in baseline characteristics are detected on other characteristics, these will be included as covariates in later analyses.

## 17. Blinding

The study statistician conducted the randomization procedure using the statistical software package R version 12.0 [ref]. For each group (a through d above), study participants will be randomized into one of the two treatment groups: patient navigation with legal aid, or standard patient navigation, using a block randomization design to ensure that some balance between treatment groups is achieved as the study progresses. Random block sizes of 2 and 4 will be employed in a random order. Within blocks of size 2, one patient will be randomly assigned to receive patient navigation with legal aid (Intervention) while the other patient will receive patient navigation only (Control). In block sizes of 4, two of the four patients will randomly be assigned to receive patient navigation with legal aid while the other two patients will receive patient navigation only.

The investigator and clinicians assessing the outcomes of the study will remain blinded to each participant's treatment group assignment until the study is completed.

The randomization scheme developed by the Biostatistician will be incorporated into the RedCap data management system. When Screening forms are entered into Redcap, those patients that enroll will be randomized based on their strata and linked to study Ids in RedCap.

Ref: *R Core Team (2012). R: A language and environment for statistical computing. R Foundation for Statistical Computing, Vienna, Austria. ISBN 3-900051-07-0, URL <http://www.R-project.org/>*

Assignment of Study ID- each patient that is eligible and has signed a consent form, will be entered into the RedCAP project for the study, confirming eligibility before the system randomizes participant into the intervention or control group. The patient will be assigned a unique 4 digit study id. The first digit will identify which cancer type the patient has been diagnosed with (1 for Breast, 2 for Lung) and then numbers will be assigned in sequential order.

- Ex: The 5th Breast cancer participant will have Study ID 1005
- Ex: The 29th Lung cancer participant will have Study ID 2029

# Data collection, management, and analysis

## 18. Data Collection

### General Instructions for Completing Forms

- Forms completed by the participant:
  - Surveys will be administered by the study RA
  - RA will speak with patient preferably in person but possibly over the phone to administer surveys.
  - The RA will verbally ask the patient each question on the surveys, to ensure consistency in understanding and account for differences in literacy levels of study participants.
  - Responses will be marked on survey instrument and returned to office for data entry and proper storage.
  - Before completing the interview session the RA will review the surveys to ensure there are no missing items or data, and if any items were left blank the RA will follow-up with the participant before the end of their meeting to collect any missing data
- Forms completed by research personnel:
  - Screening information, clinical abstractions will be completed by trained research personnel
  - Training- study team members will be trained on abstracting relevant data from the Electronic Medical Record. Training will cover basic cancer care and treatment as well as how to review an electronic medical chart and identify key clinical data elements for data collection
  - Adjudication/quality review- to ensure quality data a clinical\_adjudication team will review and confirm key clinical data elements. Key variables will be abstracted by a second abstractor, results compared and discrepancies flagged for resolution by Data Manager

## 19. Data Management

### Missing data/integrity of data

Every six months data will be reviewed by the Data Manager, the Biostatistician and the Analyst to determine if any patterns for missing data are present. If issues are found, adjustments will be made to the training and data collection protocol.

### Retention

To minimize attrition research assistants worked with each patient's schedule to identify a convenient meeting time for the patient to complete his/her surveys. Patients had the option of completing follow ups in person or over the phone. The flexibility of the research assistants coupled with their language concordance with the patients and incentives provided after each follow-up, contributed to study retention and high follow up rates.

### REDCap Data management system

REDCap is a password protected, HIPAA compliant, web-based application for building and managing online surveys and databases. It also has the ability to track and report on study progress at the participant level as well as the study level. Data Collection forms will be entered onsite through REDCap by a trained member of the research staff. For quality assurance purposes, 10% will be verified by a second staff member.

### **Data Storage**

All paper data collection tools will return to the WHU office after completion. They will be stored in a secure, locked cabinet within the office, only accessible to study staff with ID access and will be retained for 7 years after the last participant has completed the project.

## 20. Statistical methods

**Population under study:** Patients newly diagnosed with breast or lung cancer at BMC who volunteer to participate in the study and complete the I-HELP general legal screen at baseline to indicate the presence of legal need.

### **Analysis**

**Primary Clinical Outcomes: To measure the impact of patient navigation enhanced by MLPB intervention on *receipt of timely and quality cancer care*:**

- Our primary analysis will use multiple logistic regression models to compare the proportion of patients with *timely initiation of treatment* across study groups, adjusting for the influence of race/ethnicity (white vs non-white), cancer site, insurance status (private vs public), and other covariates that may have a significant effect on the outcome and may be unbalanced across the two study groups.
- Study groups will also be compared on the secondary clinical outcome of *time to initiation of primary cancer treatment* (the number of days from diagnosis to start of treatment) through Kaplan-Meier survival curves (unadjusted analyses) and Cox proportional hazards regression models controlling for cancer site and other covariates (adjusted analysis).
- *Receipt of quality care* for each cancer type will be analyzed through logistic regression.
- For the analysis of the rate of missed appointments, patients will differ on the number of scheduled appointments over the study period. We will generate summary measures of the rate and total numbers of missed appointment for the total study cohort and by treatment group.
- The primary analysis will include only participants who have legal issues at baseline (defined by the results of their baseline I-HELP general legal screen, which will take place within one month of new diagnosis). This will be the official sample of patients which the sample size calculations are based (n=117 in each group adjusting for 10% dropout).

**Secondary outcomes: To measure the impact of patient navigation enhanced by MLPB intervention on patient-reported outcomes: *distress, needs, and satisfaction*:**

- Patient-reported outcomes will be measured at baseline, 3 month follow-up, 6 month follow-up, and 12 months using summation scores with established subscales.
- Multiple linear regression models controlling for baseline levels of the outcome (i.e., analysis of covariance models) will be used to compare study groups on changes in *distress* and *psychosocial needs* at follow-up. Multiple linear regression models will also examine intervention effects on *satisfaction* scores.
- Covariates in each model may include age, race/ethnicity, stage of disease, and other covariates that may have a significant effect on the outcome and may be unbalanced across the two study groups.

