Unmet essential needs that often involve socio-legal barriers are reflected in the acronym **I-HELP** initially published in *Pediatrics* in October 2007: **I**ncome supports & Insurance; **H**ousing & Utilities; **E**mployment & Education; **L**egal Status; **P**ersonal & Family Stability/Safety (42). Each category reflects basic life needs that, if not met, may affect health and may be amenable to direct legal advocacy or service intervention should initial efforts by patients/families to satisfy these needs be unsuccessful.

Data from the National Patient Navigation Research Program (PNRP), the largest multi-site study of navigation in cancer care to date, documents the impact socio-legal barriers have on equitable cancer

care. Using a list of 20 discrete barriers to care (43), PNRP navigators were also trained to document reported patient barriers to care during each patient encounter.

Analyses found that navigated patients with documented barriers to care experience less timely resolution of their screening abnormalities; the more barriers present, the less timely their care (44). In a secondary analysis, we categorized barriers into two groups: 1) socio-legal barriers and 2) other barriers. Among 1,493 patients receiving navigation, only 6% had socio-legal barriers to care documented by the navigator. The top 3 barriers documented by navigators were: language issues (25%), scheduling issues (14%), and fear (12%). Yet, those with socio-legal barriers to care were less likely to have timely resolution of diagnostic care (aHR: 0.51, 95% CI: 0.39, 0.66) compared to those with other barriers, even when accounting for the presence of multiple barriers. This is one of the most robust findings in the Boston PNRP dataset, and a stronger predictor of delay in treatment than insurance status or race and ethnicity (45).

These findings are supported by other navigation studies that report outcomes are limited by housing, insurance and financial needs (46-48). **Therefore, it makes sense that navigation had only a modest effect in our low-income population in prior navigation studies, as navigators were not trained to identify or address these complex socio-legal barriers to care with remedies external to the healthcare system.**

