## 8. Trial Design

Randomized controlled trial

- N= 374 newly diagnosed breast & lung cancer patients
- 187= Control (standard navigation)
- 187= Intervention (MLPB enhanced navigation)

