## 12. Outcomes

### 12.1 Primary Outcomes

#### Time to first treatment

- 1) **Timely initiation of care:** The receipt of timely care will be defined as initiation of care within 90 days, as this the shortest delay that has been shown to consistently affect mortality and categorized as a dichotomous variable (yes/no). The time element will be calculated from date of diagnosis (Time 0) to date of treatment initiation (Time 1). The date chosen for the Time 1 variable will depend on the recommend care plan for each patient, as derived from the chart abstraction and based on patient presentation, including but not limited to stage at diagnosis and co-morbid medical conditions. In all cases Time 1 will be defined as the date of the first treatment **after** patient has received a definitive cancer diagnosis.
- 2) **Time to initiation of care:** continuous outcome defined as the number days from diagnosis (Time 0) to treatment initiation (Time 1).
- 3) **Rate of missed appointments:** percent of scheduled appointments that are missed over 12 month period.
- 4) **Quality of care:** Dichotomous variable (Y/N) based on select measures of quality care, as developed jointly by the Commission on Cancer, NCCN and American Society of Clinical Oncology
  - a. Measured using data abstracted from medical chart

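### The primary model lets covariates in by outcome effect and observed imbalance, instead of fixing stage and the baseline legal-need count in advance

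*Protocol*

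**What the plan says.** Section 20 (Analysis, Primary Clinical Outcomes) compares timely initiation of treatment between arms by multiple logistic regression, "adjusting for the influence of race/ethnicity (white vs non-white), cancer site, insurance status (private vs public), and other covariates". The sentence goes on to describe the other covariates as ones that might affect the outcome significantly and might be unbalanced between the groups. The Cox model for time to treatment names only cancer site, plus unnamed others. Section 16 (Allocation), item 3, says that if other baseline differences are found, those characteristics become covariates in later analyses.

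On the two covariates at issue:

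- **Stage.** Section 12.1 says the treatment date used in the endpoint follows from a care plan, abstracted from the chart and "based on patient presentation, including but not limited to stage at diagnosis and co-morbid medical conditions". In Section 20, stage appears only as a covariate that models may include, in the bullet that closes the patient-reported outcomes.
- **Number of legal needs.** Section 13 gives the I-HELP screen to all patients at baseline and again at 3, 6 and 12 months. Section 20 restricts the primary analysis to patients with a legal issue on the baseline screen. Section 6 reports from the earlier navigation programme that "the more barriers present, the less timely their care".

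**The concern.** In a randomised comparison, the reason to adjust for a baseline covariate is that it predicts the outcome. That can be judged before the data are seen. Observed imbalance is a chance event and says nothing about prognostic value. A rule that waits for imbalance has two costs.

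First, a predictor that happens to be balanced can stay out. In a logistic model, leaving out a strong predictor moves the treatment coefficient toward zero and lowers power even when the arms are balanced. The same holds in a Cox model.

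Second, the primary model is settled after looking at the data, so the primary estimate and its p-value depend on an analyst's choice.

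The I-HELP count deserves particular notice. Because everyone in the primary analysis has a legal issue, the yes/no result is constant there. Only the number of positive domains can carry prognostic information, and the primary model makes no use of it.

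**Working it through.** **Inputs.** From Section 14: "We anticipate our study will have 80% power of detecting an advantage to navigation enhanced by a medical-legal partnership", with an increase in the percentage "receiving timely initiation of care from 76% to 90.5" percent, "testing at the two-tailed .05 level". From Section 20: "n=117 in each group adjusting for 10% dropout". Allocation is 1:1 (Section 8).

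**1. The plan's own sample size.** With p1 = 0.76, p2 = 0.905, mean 0.8325 and difference 0.145:

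n = [1.960·√(2·0.8325·0.1675) + 0.842·√(0.76·0.24 + 0.905·0.095)]² / 0.145² = 103 per arm.

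Dividing by 0.9 for dropout gives 115, within two of the stated 117. With the continuity correction, n is exactly 117 before any dropout. Either way this is an unadjusted two-proportion calculation.

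**2. Power without these covariates.** Removing 10% from 117 leaves about 105 per arm. Unadjusted power (no continuity correction) is 80.8% at 105 and 84.8% at 117. The planned 80% therefore does not depend on the two covariates.

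**3. Events available.** At 105 per arm, untimely starts number 105·0.24 + 105·0.095 = 25.2 + 10.0 ≈ 35. The planned model has four terms (arm plus three), so 35/4 ≈ 9 events per term. With two more it has six, so 35/6 ≈ 6.

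**4. Size of the attenuation.** The marginal log odds ratio is ln(0.905/0.095) − ln(0.76/0.24) = 2.254 − 1.153 = 1.101. Hold these marginal rates fixed and let both covariates predict with odds ratio 2. The treatment coefficient given the covariates is then 1.209; with odds ratio 3 it is 1.379. A model without them estimates about 1.101 in every case.

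**5. Power gained by adding both covariates.** The documents give no effect sizes, so these are assumptions: need count = 1 + Poisson(1.5), capped at 6; advanced stage in 35%; the same odds ratio per standard deviation of need count and for advanced stage. There were 4,000 simulated trials per row, a Wald test on arm, and a Monte Carlo error of about 0.6 point on each power. The comparison is arm alone against arm plus the two covariates.

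| Odds ratio of each | 105 per arm | 117 per arm |
|---|---|---|
| 1.0 | 81.9% → 81.5% | 84.6% → 84.4% |
| 1.25 | 81.4% → 81.5% | 85.2% → 85.7% |
| 1.5 | 81.9% → 82.7% | 85.5% → 86.0% |
| 2.0 | 81.5% → 84.0% | 85.1% → 88.7% |
| 3.0 | 82.2% → 88.9% | 85.7% → 91.4% |

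**6. The same with the three planned covariates already in the model** (arm plus three terms against arm plus five, 105 per arm):

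| Odds ratio of each | Planned three | Plus stage and need count | Change (points) |
|---|---|---|---|
| 1.0 | 80.9% | 80.5% | −0.4 |
| 1.5 | 82.2% | 83.1% | +0.9 |
| 2.0 | 80.5% | 84.2% | +3.7 |
| 3.0 | 81.7% | 89.5% | +7.8 |

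The two comparisons agree. The loss is negligible if the covariates are weak, and the gain is modest unless both are strong.

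**The case against.** **The model does not shut these covariates out.** A reader might infer that the primary model omits stage and need count. The documents do not support that: the open clause could admit either. Its two conditions can also be read loosely rather than as a strict pair. This stands, and the fault is that nothing fixes the covariates in advance. The looser reading does not remove it, because selection by significance is also made after seeing the data.

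**A covariate list is commonly left to the SAP, which is not shown.** True, and a missing list alone would be no finding. But the protocol states a selection rule, in Sections 16 and 20, and it is the rule that is poorly chosen.

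**The evidence that these covariates predict timely treatment is indirect.** A reader might take the protocol to name them as predictors of the endpoint. It does not. The gradient in Section 6 counts barriers of every kind, and its outcome is resolution of screening abnormalities. The adjusted hazard ratio of 0.51 there contrasts types of barrier, which is largely held constant when only patients with a legal issue are analysed. Section 12.1 ties stage to the care plan but gives no direction or size for an effect on starting within 90 days. All of this stands; both covariates are plausible rather than proven.

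**Stage is not among the baseline forms.** This also stands. Section 13 does not list it; it comes from chart abstraction, whose timing is not stated. It can still describe the patient at diagnosis if defined that way.

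**The gain may be smaller, and events are few.** If stage or need count correlates with site, race or insurance, less is gained than shown. About six events per term is thin, but step 6 includes that cost and finds a loss of only 0.4 point when neither covariate predicts.

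**Conclusion.** The concern holds as a weakness in how the primary model's covariates are chosen. Imbalance should not decide what enters, and two plausible baseline covariates that the trial already collects are left to that choice.

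The size cannot be derived from the documents. Under the assumed distributions, fixing both covariates is worth about 0 to 1 point of power for odds ratios up to 1.5, 2 to 4 points at 2, and 6 to 8 points at 3. The power figures are for the logistic model only; the Cox model was not simulated. The benefit of removing a data-dependent choice from the primary analysis rests on no assumed odds ratio.

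A reader might infer that the trial is underpowered as planned. It is not on this ground: unadjusted power is 80.8% at 105 per arm and 84.8% at 117. Nor is the I-HELP screen used only to select patients, since it is repeated at follow-up and socio-legal barriers are among the study's stated aims.

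**What to change.** In Section 20, replace the clause on other covariates, for both the logistic and the Cox model, with a fixed list applied regardless of observed balance:

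- race/ethnicity, cancer site and insurance, as now;
- stage at diagnosis, early versus advanced (one term), taken from chart data at diagnosis, with the cut defined in advance for each cancer site;
- baseline number of positive I-HELP domains, entered linearly.

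Amend Section 16, item 3, so that baseline differences are described but do not change the primary model. Make the change before outcomes are examined by arm.

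The cost is a short edit and no new data collection. Statistically it is two more terms against about 35 expected untimely starts, with a power loss under 0.5 point if neither covariate predicts.

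### Kaplan-Meier is named for time to treatment start although death can preclude the event; with the usual censoring at death, the day-90 value slightly overstates initiation and will not match the yes/no endpoint

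*Protocol*

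**What the plan says.** Section 12.1 defines two outcomes from the same dates. One is yes/no: "The receipt of timely care will be defined as initiation of care within 90 days". The other is the time itself, a "continuous outcome defined as the number days from diagnosis (Time 0) to treatment initiation (Time 1"). For both, "In all cases Time 1 will be defined as the date of the first treatment" after a definitive diagnosis.

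Section 14 bases the sample size on the yes/no version, "a dichotomous outcome (yes/no) calculated for each subject", with the share "receiving timely initiation of care from 76% to 90.5" percent. It then carries these two percentages into an exponential survival model to give a log-rank power. It expects no loss to follow-up on clinical outcomes because they come from the medical record. It does not mention death.

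Section 20 makes logistic regression of the yes/no outcome the primary analysis. It continues: "Study groups will also be compared on the secondary clinical outcome of" time to initiation, "the number of days from diagnosis to start of treatment) through Kaplan-Meier survival curves (unadjusted analyses"), with Cox regression for the adjusted analysis. Section 12.1 lists the same time outcome under primary outcomes.

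Section 10 admits newly diagnosed lung or female breast cancer. It excludes small cell lung cancer and sets no stage limit.

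**The concern.** A patient who dies before any treatment has no treatment date and can never acquire one. Death is therefore a competing event and not ordinary censoring. In standard use Kaplan-Meier censors such a patient at death, and the curve then estimates initiation as though those who died would have gone on to start treatment at the rate of those still alive. The yes/no outcome, read plainly, counts the same patient as not having started in time.

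The two displays would then give different 90-day percentages for the same patients, with the curve reading higher. Section 14 treats the two as one quantity when it feeds the yes/no percentages into a survival model. That identity holds only if nobody dies untreated, or if untreated deaths are kept at risk as non-initiators. At stake is the level of a reported curve and its agreement with the headline proportions. The validity of the primary test is not in question.

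**Working it through.** **Inputs.** 90-day initiation of 76% (control) and 90.5% (intervention), two-sided 0.05, 80% power, 86% log-rank power and the constant-hazard assumption are from Section 14. The 117 per group with 10% dropout is from Section 20. The documents give no rate of death before treatment, so a 90-day death risk *d* of 1%, 2%, 5% and 10% is assumed. Here *d* is the risk of dying by day 90 if treatment start is ignored.

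**The plan's own figures.** 117 × 0.9 ≈ 105 evaluable per group gives 80.8% power for 76% against 90.5%, so the stated 80% reproduces. Under exponential times the hazard ratio is ln(1 − 0.905) / ln(1 − 0.76) = 1.65. With 105 × (0.76 + 0.905) ≈ 175 events by day 90, the Schoenfeld formula gives 91.1% log-rank power, not the stated 86%. That is a separate matter and is not used below.

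**Step 1: hazards.** Cumulative treatment hazard to day 90: T = −ln(1 − p), which is 1.427 for p = 0.76 and 2.354 for p = 0.905. Cumulative death hazard: D = −ln(1 − d).

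**Step 2: what each method reads at day 90.** With deaths censored, one minus Kaplan-Meier is p. The share who actually start treatment is the cumulative incidence:

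CIF = T / (T + D) × [1 − (1 − p)(1 − d)]

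Example, p = 0.76 and d = 0.05: D = 0.0513; CIF = 1.427 / 1.478 × (1 − 0.24 × 0.95) = 0.9653 × 0.772 = 0.745. The gap is 76.0 − 74.5 = 1.5 points.

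| Assumed 90-day death risk, both arms | Control CIF (KM 76.0%) | Gap | Intervention CIF (KM 90.5%) | Gap | Difference in CIF (KM 14.5) |
|---|---|---|---|---|---|
| 1% | 75.7% | 0.3 | 90.2% | 0.3 | 14.5 |
| 2% | 75.4% | 0.6 | 89.9% | 0.6 | 14.5 |
| 5% | 74.5% | 1.5 | 89.0% | 1.5 | 14.5 |
| 10% | 73.0% | 3.0 | 87.5% | 3.0 | 14.5 |

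**Step 3: unequal death risk.** From the same table, with 2% in control and 5% in intervention the actual difference is 89.0 − 75.4 = 13.6 points. Reversed, it is 89.9 − 74.5 = 15.4 points. Kaplan-Meier shows 14.5 in both cases.

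**Step 4: the other direction.** Suppose 76% and 90.5% are the true yes/no rates and 1% to 5% of an arm die untreated by day 90. The curve then reads 76.6% to 78.9% in control and 91.3% to 94.7% in intervention.

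**The case against.** **The protocol never says that deaths are censored at death.** This is correct. Kaplan-Meier does not force that choice: if untreated deaths stay in the risk set as non-initiators to the horizon, the curve agrees with the yes/no endpoint. The censoring rule may stand in a statistical analysis plan that is not shown, so its absence from the protocol is not the point. What remains is that the protocol names an estimator whose usual application gives the wrong level here.

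**Eligibility limits the problem.** Patients must be receiving cancer treatment at the centre, small cell disease is excluded, and patients must survive to consent. This keeps untreated deaths low but not at zero. Section 15 has patients approached on the day of diagnosis or soon after, and Section 14 assumes that 24% of controls are still untreated at day 90. The criterion can therefore hardly mean that treatment has already begun.

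**A reader might infer a much larger bias, unequal between arms.** Fixing the same share of untreated deaths in each arm at 2%, 5% or 10% gives overstatements of 1.1, 2.8 and 5.6 points in control and 1.5, 3.8 and 7.7 in intervention. That reading is not supported. Because treatment starts faster in the intervention arm, equal shares require a death hazard about 40% higher there. The implied 90-day death risks are 3.7% against 5.2%, 9.3% against 12.7%, and 18.3% against 24.7%, for whole arms that include breast cancer patients. Nothing in the documents suggests this.

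**A reader might also infer that the treatment comparison is invalid.** It is not. The primary logistic regression does not use the curve, and Cox and log-rank compare cause-specific hazards validly with deaths censored.

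**Conclusion.** The point holds as a minor improvement. Kaplan-Meier, used in the usual way, is not the right display for an event that death can preclude, and its day-90 value would exceed the share who start treatment. Under constant hazards and an equal 90-day death risk of 1% to 10%, the excess is about 0.3 to 3.0 points in each arm and the between-arm difference stays at about 14.5 points. The difference would move only if untreated deaths differed by arm, by about a point either way for 2% against 5%. The size rests on assumed death risks and on censoring at death, which is standard practice but is not stated in the protocol. No planned test is shown to be wrong.

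**What to change.** In Section 20, replace the Kaplan-Meier display with cumulative incidence curves for treatment start, with death without treatment as a competing event. Keeping untreated deaths at risk as non-initiators to the horizon gives the same day-90 value and would also do. In Section 12.1, state that a patient who dies untreated by day 90 counts as not timely. Keep the Cox model and the log-rank test, and label both as cause-specific comparisons.

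The cost is a few lines of text and a standard routine. Date of death must be abstracted from the medical record if that is not already done, since the protocol does not list it. The 90-day percentages on the curve will read slightly lower, but they will then be on the same footing as the primary proportions.
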